4.3. Prior / Concomitant Medication

Medications/Procedures will be recorded from the day of informed consent until the end of study (EOS) visit. Medications will be coded to the ATC level 2 (therapeutic main group) and ATC level 4 (chemical/therapeutic subgroup), according to the latest available version of WHO Drug Dictionary at the coding CRO. Patients will be counted once in all ATC categories linked to the medication.

Procedures will be coded to a Preferred Term (PT), High Level Term (HLT) and associated primary System Organ Class (SOC) according to the latest available version of MedDRA at the coding CRO.

Prior medications/procedures: medications taken or procedures performed prior to the first dose of study drug.

Concomitant medications/procedures: medications taken or procedures performed following the first dose of study drug through the EOS visit.

The prior systemic corticosteroid, immunosuppressant, phototherapy use and concomitant topical steroid eye drops or cyclosporine eye drops will be adjudicated by the clinical study director and the adjudication procedure will be documented before database lock.

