4.6.2. Adverse Events of Special Interest

In this study, the adverse event of special interest (AESI) category includes:

- Anaphylactic reactions or acute allergic reactions that require immediate treatment
- Severe ISRs that last longer than 24 hours
- Mycosis fungoides or other forms of cutaneous T-cell lymphoma
- Any severe infection; any infection requiring treatment with parenteral antibiotics/anti-viral/anti-fungal agent; any infection requiring treatment with oral antibiotic/anti-viral/anti-fungal for longer than 2 weeks; any clinical endoparasitosis; any opportunistic infection
- Conjunctivitis (any type or etiology), keratitis, or blepharitis (only events that are either severe or serious or lasting ≥ 4 weeks will be reported as AESIs)

- Significant ALT elevation
 - a. ALT >3×ULN associated with total bilirubin >2×ULN; or
 - b. ALT >5×ULN in patients with baseline ALT ≤2×ULN; or
 - c. ALT >8×ULN if baseline ALT >2×ULN

The search criteria for AESIs are provided in Section 10.4.

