5.8.2. Analysis of Adverse Events of Special Interest

The adverse events of special interest (AESI) will be summarized by AESI category (see Section 10.4) and by high level term and PT.

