Keratitis	
Any of the following PTs:
 
 • Keratitis • Allergic keratitis • Ulcerative keratitis • Atopic keratoconjunctivitis • Herpes ophthalmic • Ophthalmic herpes simplex 
Note: manual adjudication of relevant PTs will be required by the study medical monitor, before database lock.

Severe ISRs that last longer than 24 hours	
- HLT = Injection site reactions
 
- Severity = “severe” or Serious AE =”Yes”
 
- AE duration ≥1 day

Mycosis fungoides or other forms of cutaneous T-cell lymphoma	
-HLT = Mycoses fungoides
 
-OR LLT = Sezary syndrome
 
-OR LLT = Cutaneous T-cell lymphoma
 
-OR PT = Cutaneous T-cell dyscrasia

Any severe infection	
-SOC = Infections and infestations
 
-Severity = “severe” OR Serious AE= “Yes”

Any infection requiring treatment with parenteral antibiotics	
SOC = Infections and infestations
 
- Action taken for AE = “medication”

	- ConMed: ATC3= “Antiinfectives” during the TEAE course (between start and stop dates), Route = IV, IM
Any infection requiring treatment with oral antibiotic/anti-viral/anti-fungal for longer than 2 weeks	-SOC = Infections and infestations -Action taken for AE = “medication” -Check CM: ATC3=” BETA-LACTAM ANTIBACTERIALS, PENICILLINS” OR “OTHER ANTIBACTERIALS” during the TEAE course (between start and stop dates), Route = PO and Treatment duration >14 days
Any clinical endoparasitosis	-HLT = Cestode infections -HLT = Helminthic infections NEC -HLT = Nematode infections -HLT = Trematode infections
Any opportunistic infection ^a a: The definition of opportunistic infections is referring to the recent consensus guidance for opportunistic infections in the setting of biologic therapy (K L Winthrop et al, 2015)	The following HLTs plus PTs -HLT = Pneumocystis infections -HLT* = Fungal infections NEC -HLT* = Pseudallescheria infections -HLT = Herpes viral infections -HLT = Paracoccidioides infections -HLT = Sporothrix infections -HLT = Cryptosporidia infections -HLT* = Trypanosomal infections -HLT* = Campylobacter infections -HLT* = Shigella infections -HLT* = Vibrio infections Plus the following PTs -Polyomavirus-associated nephropathy -BK virus infection -Cytomegalovirus infection -Post transplant lymphoproliferative disorder -Progressive multifocal leukoencephalopathy -*Bartonellosis -Blastomycosis -Toxoplasmosis

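### Two AESI definitions are not carried into the SAP 10.4 search rules: the oral-treatment row omits antivirals and antifungals, and acute allergic reactions have no row, so both categories can be undercounted (minor).

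*SAP*

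**What the plan says.** SAP 4.6.2 restates the AESI list of protocol 9.4.3 and refers to Section 10.4 for the search criteria. SAP 5.8.2 then says that AESIs "will be summarized by AESI category (see Section 10.4) and by high level term and PT". Section 10.4 therefore governs what the AESI table contains.

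Two definitions in 4.6.2 matter here:

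- "Anaphylactic reactions or acute allergic reactions that require immediate treatment"
- "any infection requiring treatment with oral antibiotic/anti-viral/anti-fungal for longer than 2 weeks"

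In 10.4 the oral-treatment row carries the full label. Its medication condition is an ATC3 class of "BETA-LACTAM ANTIBACTERIALS, PENICILLINS" or other antibacterials, by mouth, for more than 14 days. The parenteral row just above it searches the general anti-infective class, taken "during the TEAE course (between start and stop dates), Route = IV, IM". The only allergic row is for anaphylactic reactions, found by a standardised query algorithm.

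The opening text of 10.4 concedes that the criteria may be incomplete. It allows, but does not require, a further blinded review of preferred terms by the medical monitor.

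**The concern.** The incidence of treatment-emergent AESIs, to week 16 and to week 36, is a secondary safety endpoint in protocol 4.2.2. A search rule narrower than the definition it implements leaves qualifying events out of the table, and the reader of the table cannot see that. Hypothesis testing has been removed and REGN3500 development continues in other diseases (SAP 1.1), so description of safety is one of the main remaining uses of this study.

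Nothing suggests that the narrowing was intended. SAP 1.2.4 lists what was dropped after the study was stopped, and the AESI definitions and analyses are not on that list.

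**Working it through.** The plan gives no figure to reproduce. The check sets definition against search rule.

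| Defined in SAP 4.6.2 | Searched in SAP 10.4 | Coverage |
|---|---|---|
| Oral antibiotic, over 2 weeks | Two antibacterial terms, oral, over 14 days | searched |
| Oral antiviral, over 2 weeks | no class listed | none |
| Oral antifungal, over 2 weeks | no class listed | none |
| Anaphylactic reactions | Query algorithm plus adjudication | searched |
| Acute allergic reactions needing immediate treatment | no row | none |

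Section 10.4 has 11 rows: anaphylaxis, conjunctivitis, keratitis, injection site reactions, cutaneous lymphoma, severe infection, parenteral treatment, oral treatment, endoparasitosis, opportunistic infection and ALT. Four carry a required adjudication note: anaphylaxis, conjunctivitis, keratitis and the starred opportunistic terms. The oral row has none.

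**Can another row find the infection?** Consider a non-serious, non-severe infection treated by mouth with an antifungal or antiviral for more than 14 days. The severe-infection row needs severe or serious. The parenteral row needs IV or IM. The opportunistic row finds it only if its term is listed, for example "HLT = Herpes viral infections". If that row does find it, the patient counts as having an AESI, but under a different category. Otherwise the event is not retrieved.

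**Can the anaphylaxis row find the allergic reaction?** The algorithm needs a Category A term, or B with C, or D with B or C. The row's own example places urticaria in Category C. Urticaria alone, treated at once, meets none of the three branches. Adjudication on that row is required for the relevant terms, but it is not stated to reach terms that the algorithm did not retrieve.

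**Where else would the events be seen?** Protocol 7.4.2.1 permanently stops dosing for an infection needing oral or parenteral antifungal or antiviral treatment of any duration, and for one needing oral antibiotics beyond 14 days. Together these cover the whole oral-row definition while dosing continues, and SAP 5.8.1 tabulates events leading to permanent discontinuation. That route closes once dosing has ended. The sponsor moved every patient still on treatment into the 20-week follow-up (SAP 2.1).

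**Scale of one event.** The safety analysis set size is not given. At most it is the 129 randomised; 110 is assumed here only as a lower illustration. With an even split over 5 arms:

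- Per arm: 129 / 5 = 25.8, and 1 / 25.8 = 3.9 percentage points; 110 / 5 = 22.0, and 1 / 22.0 = 4.5 points.
- Pooled REGN3500: 129 × 4/5 = 103.2, and 1 / 103.2 = 1.0 point; 110 × 4/5 = 88.0, and 1 / 88.0 = 1.1 points.

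This is the effect of one missed patient with no other event in the category (or, for overall AESI incidence, no other AESI). It is not an estimate of how many are missed.

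**The case against.** The best defence is that 10.4 calls itself an aid to identification, that 4.6.2 remains the definition, and that a blinded term review can pick up what the search misses. For allergic reactions this has some force, since a preferred term can flag a candidate event. But the review is optional, and for the oral row a preferred term shows neither drug class nor treatment duration. Sites must also report every AESI to the sponsor within 24 hours (protocol 9.4.3). SAP 4.6.2 and 5.8.2 do not say that those reports feed the table. They do not say that the reports are ignored either, and that should not be inferred from silence.

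The defence is right about impact. All analyses are descriptive, events are tabulated by system organ class and preferred term in both periods, and the discontinuation table covers the oral-row infections during dosing. Protocol 7.4.2.1 also stops dosing for anaphylaxis or another severe systemic reaction to the injection, which covers part of the allergic gap.

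A reader might infer several stronger points that the documents do not support:

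- *Long courses of non-penicillin antibacterials are missed.* On the text alone, the second search term may mean every antibacterial other than penicillins. Reading it as a narrow class needs the drug dictionary, which is not reproduced.
- *The ATC3 search cannot be run.* SAP 4.3 names levels 2 and 4, but does not say that level 3 is unavailable.
- *High ALT values disappear.* The ALT row does require one preferred term first. However, SAP 5.8.3 and 10.3 tabulate ALT bands and combined ALT or AST with bilirubin from laboratory values, whatever term was used, so much of this is shown anyway.
- *The keratitis and injection site rows also undercount.* They are broader than their definitions. For eye events 4.6.2 admits "only events that are either severe or serious or lasting" at least 4 weeks; the keratitis row omits that filter but requires adjudication. The injection site row accepts serious as well as severe, from 1 day. Both over-retrieve.

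**Conclusion.** The point holds as a minor defect. Followed as written, 10.4 searches one of three drug types in the oral-treatment category and one of two parts of the allergic category, and 5.8.2 carries both gaps into the AESI table. The possible error is an undercount in these two categories, and in overall AESI incidence for a patient whom no other row identifies.

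The residual gap is mainly infections arising in follow-up and acute allergic reactions that did not stop treatment. This conclusion assumes that the table is programmed from 10.4 without the optional review or reconciliation with site reports, and that the discontinuation criteria are applied during dosing.

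A reader might go on to infer that events were missed or that the safety description is unreliable. The documents show no affected event and give no event rate, so neither inference is supported.

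**What to change.** Before database lock:

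1. Add systemic antiviral and antifungal classes to the oral row. Confirm that the listed antibacterial terms cover all systemic antibacterials at an ATC level held in the coded data.
2. Add a row for acute allergic reactions, for example using the narrow Hypersensitivity query already named in SAP 5.11.2, with blinded adjudication of whether immediate treatment was required.
3. State in SAP 5.8.2 that the tabulated AESIs are reconciled with those reported by sites under protocol 9.4.3.

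As minor alignment only: derive ALT AESIs from laboratory ALT, bilirubin and baseline ALT whatever adverse event term was used, and match the keratitis and injection site rows to their definitions.

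The cost is SAP wording, a little programming and some extra blinded adjudication, all on data already collected. The adjudication load cannot be sized from the documents, because they do not list the terms in the Hypersensitivity query.

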9.4.3. Other Events that Require Accelerated Reporting to Sponsor

The following events also require reporting to the sponsor (or designee) within 24 hours of learning of the event:

Symptomatic Overdose of Study Drug: Accidental or intentional overdose of at least 2 times the intended dose of study drug within the intended therapeutic window, if associated with an AE,

Pregnancy: Although pregnancy is not considered an AE, it is the responsibility of the investigator to report to the sponsor (or designee), within 24 hours of identification, any pregnancy occurring in a female during the study or within 140 days of the last dose of study drug. Any complication of pregnancy affecting a female study patient and/or fetus and/or newborn that meets the SAE criteria must be reported as an SAE. Outcome for all pregnancies should be reported to the sponsor.

Adverse Events of Special Interest: All AESI, serious and non-serious, must be reported within 24 hours of identification using the same reporting process as for SAE reporting, per Section 9.4.2. Adverse events of special interest for this study include the following:

- Anaphylactic reactions or acute allergic reactions that require immediate treatment
- Severe ISRs that last longer than 24 hours
- Mycosis fungoides or other forms of cutaneous T-cell lymphoma
- Any severe infection; any infection requiring treatment with parenteral antibiotics/anti-viral/anti-fungal agent; any infection requiring treatment with oral antibiotic/anti-viral/anti-fungal for longer than 2 weeks; any clinical endoparasitosis; any opportunistic infection

Note:

Generally, all uncommon, atypical, peculiar, or unusually persistent infections, especially viral infections, should be reported as AESIs.

- Conjunctivitis (any type or etiology), keratitis, or blepharitis (only events that are either severe or serious or lasting ≥ 4 weeks will be reported as AESIs)

Any patient who experiences an AESI related to an eye disorder will be referred to an ophthalmologist. Further evaluation of these AESIs will be performed including any additional tests, as per the discretion of the ophthalmologist.

- Significant ALT elevation
 - ALT $>3 \times$ ULN associated with total bilirubin $>2 \times$ ULN; or
 - ALT $>5 \times$ ULN in patients with baseline ALT $\leq 2 \times$ ULN; or
 - ALT $>8 \times$ ULN if baseline ALT $>2 \times$ ULN

Refer to the study reference manual/site binder or file for the procedures to be followed.

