9.4.5. Abnormal Laboratory, Vital Signs, or Electrocardiogram Results

The criteria for determining whether an abnormal objective test finding should be reported as an AE include:

- the test result is associated with accompanying symptoms, and/or
- the test result requires additional diagnostic testing or medical/surgical intervention, and/or
- the test result leads to a change in dosing (outside of protocol-stipulated dose adjustments), discontinuation from the study, significant additional concomitant drug treatment, or other therapy

Contact the Medical/Study Director in the event the investigator feels that an abnormal test finding should be reported as an AE, although it does not meet any of the above criteria.

Repeating an abnormal test, in the absence of any of the above conditions, does not constitute an AE. Any abnormal test result that is determined to be an error does not require reporting as an AE.

Evaluation of severity of laboratory abnormalities will be assessed according to the scale outlined in Section 9.5.1.

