10.4. Search Criteria for TEAE of Special Interest

The search criteria are meant to assist the process of identification of TEAE of Special Interest. However, since these criteria might not be exhaustive in some cases or may not be specific in other cases. Hence an additional blinded review of all PTs in the database may be performed by the Medical monitor, based on medical judgement, to identify any TEAE of Special Interest/TEAE Syndrome that might have been missed by the criteria or to identify any TEAE that may have been inaccurately assigned as AESI by the algorithmic search.

AESI	Search Criteria
Anaphylactic reactions	
For SMQ “anaphylactic reaction” An algorithmic approach will be used. A case must include either:
 
 1. A narrow term (a term from Category A); 2. Patient with both a term from Category B AND a term from Category C; 3. Patient with a term from Category D AND { a term from Category B - OR a term from Category C } 
For bullets 2 and 3, the search terms that are included under the SMQ for a particular event need to have the same start date (for e.g. if search shows cough (category B term) occurring at day 3 and urticaria (category C term) occurring at day 7, this event is not adjudicated as anaphylactic reaction as this is inconsistent with the clinical presentation of anaphylaxis as an acute event with simultaneous involvement of 2 or more body systems.
 
Note: manual adjudication of relevant PTs will be required by the study medical monitor, before database lock

Conjunctivitis (any type or etiology), keratitis, or blepharitis (only events that are either severe or serious or lasting ≥ 4 weeks will be reported as AESIs)	
broad CMQ conjunctivitis (Conjunctivitis, Conjunctivitis allergic, Conjunctivitis bacterial, Conjunctivitis viral, Atopic keratoconjunctivitis, Blepharitis, Dry eye, Eye irritation, Eye pruritus, Lacrimation increased, Eye discharge, Foreign body sensation in eyes, Photophobia, Ocular hyperaemia, Conjunctival hyperaemia, Xerophthalmia)
 
Blepharitis PTs (Blepharitis, blepharitis allergic)
 
AND
 
Serious AE= “Yes” OR Severity= “severe” OR lasting ≥ 4 weeks

	Note: manual adjudication of relevant PTs will be required by the study medical monitor, before database lock.

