	
 -Coccidioidomycosis -Histoplasmosis -*Aspergillus infection -Systemic candida -Oropharyngeal candidiasis -Cryptococcosis -Listeriosis -Tuberculosis -Nocardiosis -Mycobacterial infection -*Salmonellosis -*Hepatitis B -Herpes zoster -*Strongyloidiasis -Microsporidia infection -Visceral leishmaniasis -*Hepatitis C 
Note: *Blinded manual adjudication of relevant PTs under each of HLTs listed above will be required by the study medical monitor, before database locks

Significant ALT elevation
 
ALT >3×ULN associated with total bilirubin >2×ULN; or
 
ALT >5×ULN in patients with baseline ALT ≤2×ULN; or
 
ALT >8×ULN if baseline ALT >2×ULN
	
Algorithm is to first search adverse event PT term = “Alanine aminotransferase increased” and the event must meet the following: ALT>3*ULN associated with total bilirubin>2*ULN or ALT>5*ULN with baseline ALT≤2*ULN or ALT>8*ULN if baseline ALT>2*ULN

Signature Page for VV-RIM-00114774 v1.0

ESig Approval	[Redacted] 00
---------------	---------------

ESig Approval	[Redacted] 00
---------------	---------------

ESig Approval	[Redacted] -2020 12:50:19 GMT+0000
---------------	---------------------------------------

Signature Page for VV-RIM-00114774 v1.0 Approved

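### SAP 10.4 does not match the AESI definitions: the liver search can leave out laboratory-defined cases, and the keratitis row can admit non-qualifying events

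*SAP*

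**What the plan says.** **Liver AESI, definition.** Protocol 9.4.3 and SAP 4.6.2 give the same three limbs, all laboratory values:

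- (a) "ALT >3×ULN associated with total bilirubin >2×ULN; or"
- (b) "ALT >5×ULN in patients with baseline ALT ≤2×ULN; or"
- (c) ALT above 8×ULN when baseline ALT is above 2×ULN.

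No adverse event (AE) term is part of the definition.

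**Liver AESI, search.** The last row of the SAP 10.4 table reads "Algorithm is to first search adverse event PT term" and names one preferred term (PT), *Alanine aminotransferase increased*. The event found must then also meet (a), (b) or (c). No other hepatic term, grouping or laboratory search is given. SAP 5.8.2 builds the AESI summary on the 10.4 categories, by high level term (HLT) and PT.

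**Eye AESI.** SAP 4.6.2, like Protocol 9.4.3, restricts conjunctivitis, keratitis and blepharitis: "only events that are either severe or serious or lasting" at least 4 weeks count. The conjunctivitis/blepharitis row of SAP 10.4 carries that condition. The separate keratitis row says "Any of the following PTs" and lists six terms with no severity, seriousness or duration condition.

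**Surrounding rules.**

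- On investigator reporting, Protocol 9.4.3 states: "All AESI, serious and non-serious, must be reported within 24 hours of identification".
- On abnormal tests, Protocol 9.4.5 states: "Repeating an abnormal test, in the absence of any of the above conditions, does not constitute an AE".
- On back-up, SAP 10.4 states that "an additional blinded review of all PTs in the database may be performed" by the medical monitor.

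**The concern.** The definition is value-based but the search is term-based, so the two need not select the same patients. A qualifying ALT can fail the search in two ways: there is no AE record to search, or the AE is coded to a different term. The keratitis row has the opposite fault, because it is wider than the definition it serves.

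AESI incidence through week 16 and through week 36 is a secondary safety endpoint (Protocol 4.2.2). The study was stopped early and its analyses are now descriptive. However, SAP 1.1 says that REGN3500 remains in development for other diseases, so a correct safety count still has a use. With few patients per arm, the AESI table and the laboratory tables in one report could disagree over a single patient.

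**Working it through.** There is no stated figure to reproduce on this point. The check runs the written rules on hypothetical patients.

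**Liver.** Inputs are the three limbs (SAP 4.6.2), the search row (SAP 10.4) and the ALT bands for potentially clinically significant values (PCSV, SAP 10.3). The bands are: above 3 to 5 with baseline at most 3; above 5 to 10 with baseline at most 5; above 10 to 20 with baseline at most 10; above 20 with baseline at most 20. Values are multiples of ULN.

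| Baseline ALT → on-study ALT, bilirubin | Limb met | Found by 10.4: named PT | Found by 10.4: no AE record | Found by 10.4: other PT | In a PCSV ALT band |
|---|---|---|---|---|---|
| 1 → 4, bilirubin 2.5 | (a) | yes | no | no | yes |
| 1 → 6, bilirubin 1 | (b) | yes | no | no | yes |
| 3 → 9, bilirubin 1 | (c) | yes | no | no | yes |
| 6 → 9, bilirubin 1 | (c) | yes | no | no | no |

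The search finds 4 of 4 when the named term is present and 0 of 4 in each other situation. The PCSV bands flag 3 of 4 whatever the AE record, though not as AESIs. The fourth escapes because its band requires baseline at most 5. The first also meets the combined ALT/AST-and-bilirubin PCSV criterion.

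How far the PCSV tables cover each limb, if every band is produced:

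- Limb (b): all cases. Baseline at most 2 satisfies every band above 5.
- Limb (c): all cases except those with baseline above 5×ULN.
- Limb (a): all cases through the combined criterion, unless the baseline already had ALT or AST above 3×ULN with bilirubin above 2×ULN.

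SAP 10.3 requires only one ALT level and makes the others optional. If only the marked band (above 3 to 5) were produced, the ALT bands would flag 1 of the 4.

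**Keratitis.** A mild, non-serious event of 7 days and a moderate, non-serious event of 10 days both fail the SAP 4.6.2 definition, and both pass the 10.4 keratitis row. *Atopic keratoconjunctivitis* is listed in both eye rows, so the same mild, brief, non-serious event fails one row and passes the other.

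**Size of one patient.** SAP 2.1 gives 129 randomised. Assuming an even split with all treated, 129 / 5 = 25.8, or about 26 per arm, and 1 / 26 = 3.8 percentage points.

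**The case against.** The strongest reply is that an unrecorded liver case would be a reporting failure, not the normal course. Protocol 9.4.3 names these ALT thresholds and requires 24-hour reporting by the SAE route. SAP 4.6.1 counts laboratory findings that the investigator judges clinically significant as AEs. Protocol 8.2.3.5 requires repeat testing and, where needed, further investigation, and additional diagnostic testing is itself a criterion for recording an AE. This stands as a limit on frequency. It does not repair the search, which does not admit a case on the strength of an investigator's AESI report.

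A case under another term does have an AE record, so the blinded review could find it. But that review is optional and looks at PTs, so it cannot find a case with no record. The ALT row also lacks the mandatory adjudication note carried by the anaphylaxis, eye and starred opportunistic-infection entries.

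Protocol 10.4.4.1 allows AESI summaries to rest on a PT or a grouping fixed in advance. That permits a term-based table; it does not make one term equivalent to a value-based definition.

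Laboratory cases also remain visible. SAP 5.8.3 lists all laboratory parameters by patient and visit with flags. Exclusion criterion 15 further narrows the PCSV gaps, since it bars patients who meet the study-drug discontinuation criteria at baseline. This stands, but neither output counts AESIs.

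On keratitis, adjudication is required, SAP 10.4 provides for removing wrongly assigned events, and the adjoining row's title states the restriction. The omission is probably a drafting slip. Still, the row gives the adjudicator no severity or duration rule.

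**Conclusion.** The mismatch is real on both rows. As written, the liver search can omit patients who meet the definition, and the keratitis row admits events that do not meet theirs unless adjudication removes them.

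The size is modest and cannot be estimated: the documents give no rate of unrecorded or differently coded ALT elevations. The only figure available is that each patient shifts an arm's rate by about 4 percentage points, assuming about 26 treated per arm. Most omitted cases would still be seen in the PCSV tables, provided all ALT bands are produced, and in the laboratory listings.

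A reader might infer more, and the documents do not support it:

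- That liver cases will be missed. An investigator who follows Protocol 9.4.3 reports the case, and if it is coded to the named term the search finds it.
- That cases with raised ALT and bilirubin are especially likely to carry another term. Nothing in either document bears on coding frequency.
- That mild keratitis will be counted in the final table. The required adjudication may exclude it.
- That omitted cases vanish from the report. They drop out of the AESI count, not out of the laboratory output.

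**What to change.** 1. Identify the liver AESI from central-laboratory ALT, total bilirubin and baseline ALT for every patient in the safety analysis set, in union with AESIs reported by investigators, whatever the PT.
2. List laboratory-positive patients without an AESI report, and query them before database lock.
3. Add a laboratory-only line to the SAP 5.8.2 summary. Such cases have no HLT or PT and would otherwise have no place in the table.
4. In the keratitis row, require the event to be serious, graded severe or at least 4 weeks long, in the same form as the conjunctivitis/blepharitis row.

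All the data are already collected. The cost is edits to two rows of SAP 10.4 and to SAP 5.8.2, a small amount of programming and one query listing. The liver AESI count may rise slightly.
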